6.3 Sample Size Determination

Power for the co-primary endpoints was assessed using a bootstrap simulation. To accurately model within-subject correlation across lesions, the safety and efficacy outcomes for subjects with at least 4 lesions in a previous study (SH-009) were sampled with replacement. An assumed mapping was created between the clearance scale used in that study (**Section 6.7**) and the GAIS scale: lesions rated as “Clear” with hypopigmentation rated as “None” or “Mild” were classified as GAIS responders. Among lesions rated as “Mostly Clear” with hyperpigmentation rated as “None”, a binary random variable derived from a standard normal distribution was used to categorize 88% of these as GAIS responders with the remaining 12% categorized as non-responders. All other combinations of clearance and hypopigmentation were classified as non-responders. The resulting distribution of lesions had a GAIS response rate of 73%, which reflects discounts for both conversion to a different scale and a slight reduction in efficacy due to visibility differences in photo review compared to live assessment. Both primary safety outcomes (skin texture changes at 30 days post last treatment and pigment changes or scarring at 60 days post last treatment) were also calculated for each lesion.

For each simulation, subjects were selected from SH-009 with replacement. Half of the lesions for each selected subject were randomly assigned to each treatment, which assumes equal efficacy and safety across treatments. The GEE models for the primary safety and primary efficacy outcome were used as described in **Sections 6.1.1 and 6.1.2**. The proportion of simulations for which the 95% CI for the difference in proportions excluded the critical values for the hypotheses in **Sections 6.1.1 and 6.1.2** was calculated. This analysis (based on 10,000 simulations) demonstrated that 240 lesions (approximately 48 subjects) would provide at least 80% power for the coprimary endpoint hypothesis tests. To account for error in estimation of the mapping between lesion clearance and GAIS, a target of 260 lesions (approximately 52 subjects) with follow-up at 60 days after the last treatment was set for adequate power. Assuming 10% loss to follow-up, up to 60 subjects will be enrolled.

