3.3 Randomization

All enrolled subjects will be randomized to receive the two treatments in a split-face design with CellFX being used on only one side of the face and Electrodesiccation on the other side. Randomization will be implemented through the Electronic Data Capture (EDC) system. The randomization assignment will include the type of treatment and which side of the face to treat first. For example: 1) First Treatment = CellFX and 2) Side of Face = Right. All randomized subjects will be included in the intent-to-treat analysis.

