6.1.2 Primary Effectiveness Endpoint

The primary effectiveness endpoint is response measured by the Global Aesthetic Improvement Scale (GAIS) at 60 days following the last CellFX or Electrodesiccation treatment (60 days post-last treatment). GAIS score will be assessed by three independent observers, blinded to treatment assignment, who will classify the response for each lesion based on photographs taken at baseline and 60 days post last treatment. The 3 observers will assign a score based on the 5-level GAIS scale described in this section. For analysis purposes, the lesion will be classified as a responder if 2/3 blinded observers assign a score of 4 or 5, and as a non-responder if 2/3 blinded observers assign a score of 1, 2 or 3. The timing of the evaluation of this endpoint is lesion specific as some lesions may not require a second treatment with the CellFX System or Electrodesiccation. The GAIS scale²² describes aesthetic changes as follows:

GAIS Rating	Description
5=Much Improved	Marked improvement in appearance from the initial condition, touch-up treatment(s) is not indicated
4=Improved	Obvious improvement in appearance from the initial condition, but a touch-up or re-treatment is indicated
3=No Change	The appearance is essentially the same as the original condition
2=Worse	The appearance is worse than the original condition
1=Much Worse	The appearance is much worse than the original condition

The primary effectiveness endpoint is lesion-level GAIS response, defined as a score of 5 ("Much Improved") or 4 ("Improved") versus non-response defined as a score of 3, 2 or 1 ("No Change", "Worse", "Much Worse") for at least 2/3 blinded observers. This dichotomization of the GAIS scale has been used to define response in several previous cosmetic procedures.²³⁻²⁶

The 15% non-inferiority margin for the primary effectiveness endpoint is justified by consistency of treatment and ease of use with the CellFX system. Outcomes for standard of care Electrodesiccation procedures depend heavily upon operator skill and experience. Furthermore, electrodesiccation involves destruction of the entire gland but can lead to sequelae such as scarring and discoloration. Therefore, depending on the number of lesions and the cosmetic concerns of the patient, it may be necessary to avoid such interventions.²⁷ In contrast, the CellFX system is designed to be a straightforward procedure that is reproducible among providers with fewer sequelae.

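### Is the stated power of at least 80% too high because the simulation split lesions at random while the trial allocates whole sides of the face?

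*Combined protocol and SAP*

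**What the plan says.** Section 6.3 resamples SH-009 subjects with at least four lesions, with the stated aim "To accurately model within-subject correlation across lesions". After mapping the clearance scale to GAIS, "The resulting distribution of lesions had a GAIS response rate of 73" percent. Treatment labels were then assigned within subject: "Half of the lesions for each selected subject were randomly assigned to each treatment, which assumes equal efficacy and safety across treatments". From 10,000 simulations the section concludes that "240 lesions (approximately 48 subjects) would provide at least 80% power for the coprimary endpoint hypothesis tests". It then allows for error in the scale mapping: "a target of 260 lesions (approximately 52 subjects) with follow-up at 60 days after the last treatment was set for adequate power". With 10% loss to follow-up, up to 60 subjects are enrolled.

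Section 3.3 allocates by side, with "CellFX being used on only one side of the face and Electrodesiccation on the other side". Section 1.5 describes SH-009 as a dose-response study of nano-pulse stimulation and mentions no electrodesiccation group. Section 6.1.2, in justifying the margin, says: "Outcomes for standard of care Electrodesiccation procedures depend heavily upon operator skill and experience". It continues: "In contrast, the CellFX system is designed to be a straightforward procedure that is reproducible among providers with fewer sequelae". Section 3.5 says that electrodesiccation is standardised across sites, with a training video.

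**The concern.** Section 6.3 discloses one assumption, equal efficacy and safety. Random labelling of lesions that all had the same type of treatment carries a second one, which is not stated: same-treatment and cross-treatment correlation are equal. In a split-face comparison the subject effect cancels from the treatment difference only to the extent that the two sides share it. If a subject's electrodesiccation lesions share something that the CellFX lesions do not, part of that variation stays in the difference and power falls. Section 6.1.2 gives a reason to expect this for electrodesiccation.

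The 240- and 260-lesion targets rest on the simulated figure, and the step between them is already assigned to mapping error. All three co-primary endpoints must succeed (section 6.1), and section 6.3 does not say in so many words whether the 80% is joint. If the figure were materially too high, the trial could miss non-inferiority for lack of precision.

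**Working it through.** **Inputs from the documents.** Margin 15 points and one-sided 2.5% test (sections 6.1.2 and 6.1.3). Response 73% in both groups, 240 lesions in 48 subjects and 260 in 52, so 5 lesions per subject and m = 2.5 per side (section 6.3).

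**Assumptions.** GAIS is the limiting endpoint. The correlations are not given and are set below.

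**Formulas.** For S subjects, Var(difference) = [2 × 0.73 × 0.27 / (S × m)] × DF, and power = Φ(0.15/SE − 1.96).
- Random lesion split with common correlation r: DF = 1 − r.
- Whole sides: DF = 1 + (m − 1) × r_same − m × r_cross, with r_same averaged over the two treatments.

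**Step 1: the plan's figure.** The SH-009 data are not in the documents, so the bootstrap cannot be re-run. With independent lesions (DF = 1) and S = 48, SE = √(0.3942/120) = 0.0573 and power is 74.4%. Power of 80% needs DF = 0.873, a common correlation of 0.127. A common correlation of 0.2 gives 83% and 0.3 gives 88%. The stated floor therefore holds on GAIS for any common correlation of about 0.13 or more, provided it cancels fully between sides.

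**Step 2: whole-side allocation.** Let the excess be same-treatment minus cross-treatment correlation. Its effect depends on where it sits:
- Electrodesiccation lesions only: averaging over treatments halves it, so DF rises by (1.5/2) × excess = 0.75 × excess.
- Both sides, with likeness by side already averaged into the SH-009 correlation: DF rises by 1.875 × excess.
- Both sides, with cross-treatment correlation below the SH-009 value: DF rises by 2.5 × excess.

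Power when calibrated to exactly 80% at 240 lesions (no excess gives 83% at 260):

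| Where the excess sits | Excess | 240 lesions | 260 lesions |
|---|---|---|---|
| Electrodesiccation only (0.75) | 0.05 | 78.3% | 81.5% |
| Electrodesiccation only (0.75) | 0.10 | 76.7% | 79.9% |
| Both sides (1.875) | 0.05 | 75.9% | 79.1% |
| Both sides (1.875) | 0.10 | 72.0% | 75.4% |
| Both sides (2.5) | 0.05 | 74.5% | 77.9% |
| Both sides (2.5) | 0.10 | 69.5% | 72.9% |

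One row worked: 0.873 + 0.75 × 0.05 = 0.910; at S = 52, SE = √(0.3942 × 0.910/130) = 0.0525, and Φ(0.15/0.0525 − 1.96) = 81.5%.

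**Step 3: scale of the excess.** It corresponds to a treatment-specific response probability varying between subjects with SD √(excess × 0.73 × 0.27): 9.9 points at 0.05 and 14.0 points at 0.10.

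**Step 4: sensitivity to the calibration.** The plan says at least 80%. If the simulated power was 85%, an excess of 0.05 leaves 82 to 86% at 260 lesions across the three patterns, and 0.10 leaves 77 to 85%. If it was 90%, 260 lesions keep 82% or more in every pattern up to 0.10.

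**The case for a change.** The strongest case for acting is that the mismatch is real, section 6.3 does not disclose it, and no stated buffer covers it. If likeness is by side for both treatments, an excess of only 0.039 (factor 1.875) or 0.029 (factor 2.5) takes power at 260 lesions below 80% under the exact-80% calibration. If cross-side correlation is half the same-side value, power at 240 lesions is 70 to 73% for same-side correlations from 0.13 to 0.4. The sponsor holds the code and the data, so a re-run is cheap.

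The direction of the bias stands; its size does not. The documents report no likeness by side and no gap between modalities. The only mechanism they offer is operator skill with electrodesiccation, which supports at most the 0.75 pattern. Even that fit is loose, because an operator's skill is shared by all of that operator's subjects, at up to five sites, rather than varying independently from subject to subject. If such effects average out over the trial's operators, a simulation with five equal sites and an operator SD of 10 points leaves power at about 79% and 82% for 48 and 52 subjects. If operators are viewed as a random sample, power falls and subject-clustered standard errors no longer guarantee the type I error. That is a question about generalising beyond these operators, and re-labelling SH-009 lesions by side would not answer it.

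The split is also favourable in correlation structure only. A true difference of zero is the usual planning assumption and is disclosed. With the 1.875 pattern, an excess of 0.10 and 260 lesions, a true CellFX advantage of 1 point on GAIS brings power back to about 80.6%.

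On joint power, section 6.3 counts simulations whose intervals excluded the critical values for the hypotheses of both 6.1.1 and 6.1.2. That can be read as joint. Saying so outright would add detail without altering the design.

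**Conclusion.** The simulation does not mirror whole-side allocation, and the stated power could be somewhat too high for that reason. No stated figure is shown to be missed. Under the only pattern with support in the documents, and with the least generous reading of the 80% floor, power on GAIS is 78.3% at 240 lesions and 81.5% at 260 for an excess of 0.05, and 76.7% and 79.9% for 0.10. At the 260-lesion target the loss against no excess is 1.6 to 3.1 points (83.0 less 81.5 or 79.9, from unrounded values), and power stays at or within rounding of 80%.

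This rests on GAIS being the limiting endpoint, 73% response in both groups, five lesions per subject and an assumed excess. SH-009 as described has no electrodesiccation lesions, so it could not supply that excess, and a re-run would return power over a range the analyst chose. The result would replace one descriptive sentence and leave the endpoints, GEE model, 60-subject cap and success rule as they are. Resampling the only data to hand, under a disclosed assumption of equal treatments, is a fair trade-off. A sensitivity run would be reasonable but optional, and the plan need not change.

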Published data from the initial use of Nano-Pulse Stimulation (NPS) technology for the treatment of sebaceous hyperplasia (SH) conducted under Protocol NP-SH-006¹³ (June 28, 2018 through November 29, 2018) in 72 subjects (Fitzpatrick Skin Types I-IV) and 226 primary treated lesions along with 18 retreated lesions at 30-days (n=244) demonstrated greater than 99% investigator rated clearance efficacy with 1 to 2 NPS sessions at 60-days post-last NPS. Efficacy was reported at 91% of treated lesions being rated clear or mostly clear at 60-days post-last NPS with a single treatment. There were no serious adverse events reported. However, in some subjects there were lesion observations of mostly mild post-treatment hyperpigmentation of 45% and skin surface irregularities of 33%. In comparison to the literature, these observations are routinely observed when using treatment modalities like laser with reported hyperpigmentation rates ranging from 30-60%¹⁵⁻¹⁶ and volume irregularity of 24%.¹⁷

In a second pivotal SH study with dose-response design¹⁸ under Protocol NP-SH-009 (July, 18, 2019 through February, 19, 2020) using much lower energy profiles (30, 60 and 115 mJ/mm³) as compared to NP-SH-006, showed efficacy rates of 82%, 81%, and 92%, respectively in 116 subjects (Fitzpatrick Skin Types II-IV) and 477 lesions at 60-days post-last NPS. Lower settings more frequently warranted another NPS session, with respective retreatment rates of 27%, 12% and 14%. For lesions treated once, lower settings showed reduced efficacy (54%, 70%, 78%) but also reduced transient PIH rates (14%, 8%, 36% - typically mild) and transient focal surface irregularities (2%, 1%, 10% - also typically mild) that resolved as normal dermis filled in the area where the SH lesion cleared. Overall subject satisfaction was relatively high for all lesions rated clear and mostly clear and treated with the 2.5x2.5mm tip at the two lowest settings with 85% of lesions rated satisfied and mostly satisfied. This study demonstrated the use of low energy settings in a single NPS session to clear a majority of lesions with a low rate of transient skin effects, while a second NPS session achieves greater than 80% clearance.

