3.7 Number of Subjects

Up to 60 subjects at up to 5 sites will be enrolled.

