4.2 Subject Selection

4.2.1 Inclusion Criteria

Candidates for this study must meet **ALL** the following criteria:

1. Subject is at least 21 and no older than 80 years of age.
2. Subject has a Fitzpatrick Skin Type I, II, or III.
3. Subject gives voluntary, written informed consent to participate in this clinical investigation and from whom consent has been obtained.
4. Subject must comply with study procedures including follow-up visits.
5. Subject is willing to have SH lesions treated in a single treatment session and understands that their lesion(s) may undergo a second treatment session at a subsequent visit.
6. Subject must have a minimum of four SH lesions and up to 10 SH lesions to be treated and the subject must have at least two SH lesions located on each side of the face.
7. For study purposes, the SH lesions must be no greater than 2 mm in height and must not exceed 5 mm x 5 mm at their largest dimension. The subject's lesions cannot be located within the eye orbit, nose, or scalp.
8. Subject consents to have photographs taken of the SH lesion(s).
9. Subject agrees to refrain from using all other lesion removal products or treatments (e.g. retinols, retinoids, and exfoliating products) to the treated SH lesions or any new SH lesions during the study period.
10. Subject agrees to refrain from prolonged sun exposure during the study period.

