4.5.3 CellFX Treatment / Electrodesiccation Treatment

- Up to 10 clinically diagnosed SH lesions that meet the study criteria will be selected by the treating investigator and prior to assigning lesions the subjects should have baseline photos taken.
- The site will log onto the Captivate EDC system. The randomization assignment will include the type of treatment and which side of the face for CellFX and Electrodesiccation.
- A template may be used to determine which treatment tip size will be used for each lesion – sizes range between 1.5 mm x 1.5 mm and 5.0 mm x 5.0 mm. The identified lesions will be numerically labeled.
- The blinded site investigator will then perform a baseline lesion(s) assessment.
- Photographic images of each selected lesion will be taken prior to using local anesthesia/numbing.
- Local anesthesia/numbing will be applied to all selected study lesions.
- Each lesion randomized to CellFX will be treated with pre-determined energy settings; each lesion randomized to Electrodesiccation will be treated as defined in **Section 3.5**.
- The subject will be asked to rate his/her pain immediately after each lesion treated with the CellFX and Electrodesiccation procedures by using a numerical rating score.
- The subjects will be asked whether they felt muscle twitching immediately after each lesion treated with CellFX.
- Post procedure lesion assessment will be performed by the blinded site investigator.
- Photographic images of each selected lesion will also be taken post-treatment.
- A light bandage and/or any physician recommended dressing may be applied before the subject leaves the clinic.
- Any adverse events will be identified and documented.

4.6. 7-Day Follow-up Visit

- Photographic images of each of the study lesions will be taken with pre and post lesion markings.
- All lesions will be clinically assessed by the blinded site investigator.
- Any adverse events will be identified and documented.

4.7 30-Day Follow-up Visit (Optional CellFX/Electrodesiccation Treatment #2)

- Photographic images of each of the study lesions will be taken with pre- and postlesion markings.
- All lesions will be clinically assessed by the blinded site investigator and rated using GAIS scale and the 4-point lesion clearance scale.
- If any lesion is rated 1-4 on the GAIS scale, a second treatment with CellFX or electrodesiccation will be performed to the previously treated lesion.

In case of a second CellFX or Electrodesiccation treatment:

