4.10 Subject Withdrawal

A study subject has the right to discontinue participation at any time without penalty or loss of benefits to which the subject is otherwise entitled. A withdrawn subject will be treated according to standard of medical care and will not be replaced.

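### Does capping enrolment at 60 subjects leave the 240- and 260-lesion power targets unsecured?

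*Combined protocol and SAP*

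**What the plan says.** Section 6.3 (Sample Size Determination) reports a bootstrap of 10,000 simulations that "demonstrated that 240 lesions (approximately 48 subjects) would provide at least 80% power for the coprimary endpoint hypothesis tests". To allow for error in mapping the earlier clearance scale to GAIS, "a target of 260 lesions (approximately 52 subjects) with follow-up at 60 days after the last treatment was set for adequate power". Enrolment follows from that: "Assuming 10% loss to follow-up, up to 60 subjects will be enrolled". Section 3.7 repeats the limit: "Up to 60 subjects at up to 5 sites will be enrolled".

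The lesion count per subject is a range. Under Section 4.2.1, "Subject must have a minimum of four SH lesions and up to 10 SH lesions to be treated", with at least two on each side of the face. Section 4.5.3 leaves the choice to the site: "Up to 10 clinically diagnosed SH lesions that meet the study criteria will be selected by the treating investigator". Section 4.10 adds that "A withdrawn subject will be treated according to standard of medical care and will not be replaced".

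The bootstrap drew from the subjects in SH-009 who had at least 4 lesions. Their mean lesion count is not reported. Section 1.5 gives only the whole-study figures for SH-009: "in 116 subjects (Fitzpatrick Skin Types II-IV) and 477 lesions at 60-days post-last NPS".

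**The concern.** The power claim and the enrolment limit are in different units, and they agree only at 5.0 lesions per subject. That figure is not stated as an assumption. A subject qualifies with 4 lesions, withdrawals are not replaced, and the supplied text has no running lesion total, no minimum mean and no provision for going beyond 60 subjects. Sites could therefore enrol the full 60, lose the planned 10%, follow the protocol exactly, and still finish below the lesion number on which the 80% rests.

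The earlier studies seem to sharpen the worry. SH-009 averaged 477/116 = 4.11 lesions per subject and SH-006 averaged 226/72 = 3.14, both under 5. All three co-primary endpoints must succeed, so a loss of power counts directly against the study. Lesion counts are also known on the day of treatment, so a shortfall could be seen in time without looking at any outcome.

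**Working it through.** **Inputs.** From Section 6.3: at least 80% power at 240 lesions (about 48 subjects), target 260 (about 52), 10% loss, up to 60 enrolled, GAIS response 73%, no true difference between treatments. From Section 6.1.2: margin 15 points, one-sided 2.5%. From Section 4.2.1: 4 to 10 lesions per subject. Not given in the documents: the within-subject correlation, the safety event rates, the power actually obtained at 240, and whether that power is joint over the three endpoints.

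**1. The plan's own figures.**
- Lesions per subject: 240/48 = 5.0 and 260/52 = 5.0.
- Enrolment: 52/0.9 = 57.8, so 58, stated as up to 60.
- Evaluable subjects: 60 × 0.9 = 54. At 5 lesions each, 54 × 5 = 270, which is 10 above the target and 30 above the 80% figure.

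The arithmetic is consistent.

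**2. Where the targets fail.** With 54 evaluable subjects:
- the 240 needs a mean of 240/54 = 4.44;
- the 260 needs 260/54 = 4.815, so about 4.82.

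A mean of 4.44 is not demanding when 4 is the floor and 10 the ceiling. If 12 of the 54 had 6 lesions and the other 42 had 4, the total would be 72 + 168 = 240. At the floor itself, 54 × 4 = 216, which is 24 below 240 and 44 below 260.

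**3. Power at other lesion counts.** With lesions split evenly within subject, the variance of the difference is proportional to 1/L, where L is the number of lesions. If P is the power at 240, then for a single test

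power(L) = Φ((1.96 + z_P) × √(L/240) − 1.96).

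| Mean, 54 subjects | L | P = 80% |
|---|---|---|
| 4.0 | 216 | 75.7% |
| 4.5 | 243 | 80.5% |
| 4.815 | 260 | 83.0% |
| 5.0 | 270 | 84.4% |

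For 216: (1.96 + 0.842) × √0.9 − 1.96 = 0.698, and Φ(0.698) = 75.7%. If P is 85%, 216 lesions give 81.1%. They still give 80% once P reaches 84.0%.

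**4. Check on the effectiveness endpoint.** With p = 0.73, correlation ρ and n lesions per arm, the variance is 2p(1 − p)(1 − ρ)/n. At 240 lesions this gives 74.4% for ρ = 0, 80.0% for ρ = 0.127, 83.3% for ρ = 0.2 and 87.9% for ρ = 0.3. On this approximation, the stated 80% or more needs ρ of about 0.127 or higher. At 216 lesions, power is 75.7%, 79.3% and 84.3% for ρ = 0.127, 0.2 and 0.3. A split-face simulation at ρ = 0.127 gave 76.8% for 54 subjects with 4 lesions, 80.2% at a mean of 4.5 and 84.4% at 5.

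**5. If the 80% is joint.** As an assumed extreme, take three independent, equally limiting tests. Each has power 0.80^(1/3) = 0.928 at 240 (z = 1.463). At 216, each has Φ(3.423 × √0.9 − 1.96) = 0.901, and 0.901³ = 73.2%, a loss of 6.8 points. The break-even means in step 2 do not change.

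**6. What the earlier averages say.** The SH-009 mean of 4.11 covers all its subjects, and the filter of at least 4 lesions in Section 6.3 implies that some had fewer. It is compatible with a mean of 5 in the filtered group: for illustration, 55.5% of subjects averaging 5 and 44.5% averaging 3 gives 2.775 + 1.335 = 4.11. The SH-006 mean of 3.14 lies below this trial's minimum and cannot occur here.

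**The case for a change.** The strongest case for a change is that the 5.0 is inferred by the reader and never stated, and that it need not carry over even if it is the mean of the filtered SH-009 group. This trial requires two lesions on each side and enrols Fitzpatrick I to III, whereas SH-009 enrolled II to IV. The step from 240 to 260 was added for a specific reason, uncertainty in the scale mapping, so a mean between 4.44 and 4.82 uses up protection that the sponsor thought necessary. Continuing until 260/0.9 = 288.9, so 289, lesions are treated would use counts only.

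Much of this stands. The planning mean and its distribution are not reported, no enforcing rule appears in the supplied text, and the slack behind the 80% cannot be quantified. None of it shows that the mean will fall short. Holding enrolment to 289 treated lesions would mean 65 subjects at a mean of 4.5 (260/4.5/0.9 = 64.2) and 73 at a mean of 4.0 (72.2). At 4.5 the existing 60 already reach 240 (240/4.5/0.9 = 59.3), so the extra subjects would defend the buffer and not the 80%. The absence of replacement is what the 10% allowance is there to cover.

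**Conclusion.** No change follows. The plan meets every figure it states at the lesion count it used, and that count has a visible basis in a source group with the same minimum as eligibility. What is missing is a reporting detail: the lesions-per-subject distribution behind the bootstrap. The sponsor can supply it and can follow the lesion total during enrolment without amending the design.

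With 60 enrolled and 10% loss, a mean below about 4.82 misses the 260 and a mean below 4.44 misses the 240. In the extreme of 4 lesions for every subject, power falls about 4 points below its value at 240 (to 75.7% if that value is exactly 80%), or up to about 7 points on the joint-power assumption in step 5. These sizes rest on an even split of lesions, variance proportional to 1/L and equal true rates in the two arms. Type I error, the margins and the GEE analysis are unaffected. Raising the cap to between 65 and 73 would expose more subjects to guard against a contingency that the documents do not show to be likely. Keeping 60 is a fair trade-off. The conclusion covers the text supplied, since Section 6.0 refers to a SAP for further detail.
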